- Number of used mapping points per minute: defined as the total number of mapping points used divided by the relative mapping time
- Substrate characteristics identified: for each type of arrhythmogenic substrate this will be defined as the frequency of substrate type identified in cases that attempted to identify the specific substrate
- Ablation strategy(s) used: defined by both the type of map used to define ablation strategy and the frequency each ablation strategy/target was used by physicians

4.2 **Outcomes Endpoint**

To quantify and characterize the acute- and long-term success rate of RF ablation after electroanatomical mapping with HD mapping catheters, the following will be summarized:

- Rate of acute success defined as the proportion of subjects who receive HD mapping and RF energy delivery resulting in acute termination of clinical arrhythmia, defined by termination to SR

Clinical Investigation Plan

(or AT if being treated for PersAF) or non-inducibility of clinical arrhythmia after ablation (cardioversion allowed prior to inducibility attempt).

- Rate of long-term success defined as the proportion of subjects who receive HD mapping and RF energy delivery with the following pre-defined procedural endpoints:

AF (utilizing a 90-day blanking period following index ablation):

- freedom from all atrial arrhythmias (AF/AFL/AT) greater than 30 seconds (as documented by 24-hr Holter at 12-month follow-up) and on or off class I/III antiarrhythmic drug (AAD).
- freedom from all atrial arrhythmias (AF/AFL/AT) greater than 30 seconds (as documented by 24-hr Holter at 12-month follow-up) and off all class I/III AADs.

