5.3.2 Inclusion Criteria

General Inclusion Criteria

1. Subject must provide written informed consent for study participation and willing and able to comply with the protocol described evaluations and follow up schedule
2. Subject must be over 18 years of age. (In Japan, the subject must be of 20 years of age or older)
3. Subject is diagnosed with AF as defined by:
 - Documented symptomatic paroxysmal AF defined as AF that terminates spontaneously or with intervention within 7 days of onset
 - Documented symptomatic persistent AF defined as continuous atrial fibrillation that is sustained beyond 7 days but less than 12 months
4. Subject is indicated for cardiac electroanatomical mapping and RF ablation procedure to treat AF
5. Subject is planned to have electroanatomical mapping performed with the HD mapping catheters under investigation

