6.0 TREATMENT AND EVALUATION OF ENDPOINTS

6.1 Baseline Visit

6.1.1 Clinical Assessments

The items listed below will be collected from each subject at the Baseline Visit. Information gathered at this visit may be used to verify eligibility of the subject for the trial.

- Documentation of the informed consent process
- Confirmation of enrollment criteria, including pregnancy test if patient is a female of child bearing potential
- Subject demographics
- Complete physical exam including height, weight, and NYHA assessment (If these assessments were performed prior to consent, they may be used if they were completed within 60-days of the ablation procedure)
- Cardiovascular disease history (most recent value prior to baseline visit)
- Arrhythmia history including documentation of AF (including paroxysmal or persistent)
- Antiarrhythmic medication – including any current class I/III AAD and dose, and history of any class I/III AAD and maximum dose
- Current anticoagulant medication

Clinical Investigation Plan

Record the required information on the appropriate CRFs. Any protocol deviations (refer to Section 10.5 for details) observed will also be recorded at this time.

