6.4 Follow-up Visits

6.4.1 Clinical Assessments

A Follow-up visit will be scheduled at 6 months (180 days \pm 14 days) and 12 months (360 days \pm 14 days) post procedure. The scheduled visit windows are calculated from the index procedure. The visit must be completed in-clinic. The following information will be collected:

- Arrhythmia recurrence
- Antiarrhythmic medications - including any current class I/III AAD and dose
- Other monitoring device source documentation of arrhythmia if applicable
- Adverse events if applicable
- Protocol deviations if applicable
- 24-hour Holter monitor (at 12-month visit only)
 - A core laboratory will review each recording and report findings to the Sponsor.

Note: The Sponsor may request access to other patient data during the required protocol follow up visits or throughout the follow up period, which may include, but is not limited to, data from implanted device(s). Record the required information on the appropriate CRF(s). Documentation of arrhythmia (e.g. ECG printouts and/or Holter reports) where applicable, should be retrieved and submitted electronically through EDC to the Sponsor.

Sponsor representatives can be involved in providing support during the follow-up procedures.

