6.5 Unscheduled Visits

6.5.1 Clinical Assessments

If a subject is seen by any physician for possible arrhythmia recurrence and/or arrhythmia associated symptoms outside of a regularly scheduled study visit and/or had an urgent care or emergency room visit regarding possible arrhythmia, these visits need to be documented as "Unscheduled Visits". Minimally, the following information should be documented for an unscheduled visit:

- Monitoring device source documentation of arrhythmia if applicable
- Antiarrhythmic medication - including any current class I/III AAD and dose
- Occurrence of any repeat ablation
- Document adverse events if applicable
- Protocol deviations if applicable

Clinical Investigation Plan

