6.7 Core Laboratory

A core lab will be used for the collection, interpretation, and collation of data collected from Holter monitoring.

The core lab will provide independent review of this data by appropriately trained personnel using standardized procedures to interpret Holter monitor tracings for adjudication of atrial arrhythmias. Findings will be communicated to the investigator and to Abbott. The core lab's adjudication findings will be used for analysis.

Clinical Investigation Plan

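### Long-term success in paroxysmal AF rests on one 24-hour Holter with no baseline episode frequency, so an unmeasured and possibly large share of unchanged AF could be scored as success

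*Combined protocol and SAP*

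**What the plan says.** **Entry.** Section 5.3.2 admits "Documented symptomatic paroxysmal AF defined as AF that terminates spontaneously or with intervention within 7 days of onset". Symptoms and an indication for mapping and RF ablation are required. A number of episodes, a frequency or a recency is not.

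**Baseline.** The only rhythm item listed in section 6.1.1, apart from medication, is "Arrhythmia history including documentation of AF (including paroxysmal or persistent"). Neither that list nor Table 2 includes a baseline Holter.

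**Endpoint.** Section 4.2, repeated in Appendix XII, offers the result as the long-term success rate of RF ablation. Its criterion is "freedom from all atrial arrhythmias (AF/AFL/AT) greater than 30 seconds (as documented by 24-hr Holter at 12-month follow-up"), under the lead-in "AF (utilizing a 90-day blanking period following index ablation").

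**Measurement.** Section 6.4.1 schedules a "24-hour Holter monitor (at 12-month visit only"). Of the Holter data, section 6.7 says: "The core lab's adjudication findings will be used for analysis".

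**Other recurrence data.** Section 6.4.1 also collects recurrence at months 6 and 12, with "Other monitoring device source documentation of arrhythmia if applicable". Section 6.5.1 has visits for possible recurrence or symptoms recorded as unscheduled visits. Section 7.3.1 treats recurrence as lack of effectiveness. Section 8.2.1 plans Kaplan-Meier analysis in which events in the first 90 days are not effectiveness failures.

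**The concern.** Paroxysmal AF is, by the plan's own definition, intermittent. A subject who is between episodes when the recording is made satisfies the rhythm criterion whether or not the ablation did anything, and could have satisfied it on the day of entry. The study has one arm, and the rhythm endpoint has no baseline reference, whereas quality of life in section 4.3 is measured as change from baseline. The listed data therefore give a reader no way to separate an effective ablation from an uninformative day of recording.

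The absence of hypothesis tests does not remove the problem, because quantifying this rate is one of the study's stated aims. The figure would be published and read as the success rate of ablation after HD mapping.

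**Working it through.** **Plan's own figure.** There is none to reproduce. The readable text gives no expected success rate and no Holter sensitivity, and the planned enrolment of about 200 has no derivation there. The point does not depend on the sample size.

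**Inputs from the documents.** One 24-hour recording at day 360 ± 14 (6.4.1); failure is any AF/AFL/AT over 30 seconds (4.2); paroxysmal episodes may last up to 7 days (5.3.2); the blanking period is 90 days (4.2, 8.2.1).

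**Assumptions, none of them in the documents.** Mean cycle between onsets T (days), episode duration d (days), and, in step 3, the chance q that an episode is documented outside the month-12 Holter. AF is taken as unchanged by the ablation.

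**Step 1. Holter alone, alternating model.** Sinus gaps are exponential with mean G = T − d, and episodes have fixed length d. A clean recording needs sinus rhythm at the start and no onset within one day:

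P(clean) = (G/T) × exp(−1/G)

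- Daily, 6 h: 0.75 × exp(−1/0.75) = 0.75 × 0.264 = 0.198
- Weekly, 6 h: (6.75/7) × exp(−1/6.75) = 0.964 × 0.862 = 0.832 (simulation also gave 0.832)
- Weekly, 24 h: (6/7) × exp(−1/6) = 0.857 × 0.846 = 0.726
- Weekly, 72 h: (4/7) × exp(−1/4) = 0.571 × 0.779 = 0.445
- Monthly, 24 h: (29/30) × exp(−1/29) = 0.967 × 0.966 = 0.934

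| Mean cycle | 1 min | 6 h | 24 h | 72 h |
|---|---|---|---|---|
| Daily | 37% | 20% | – | – |
| Every 2 days | 61% | 49% | 18% | – |
| Weekly | 87% | 83% | 73% | 45% |
| Every 2 weeks | 93% | 91% | 86% | 72% |
| Monthly | 97% | 96% | 93% | 87% |

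The pass share exceeds one half once the mean cycle is longer than about 1.4 days (1-minute episodes), 2.0 days (6 h), 3.7 days (24 h), 7.8 days (72 h) or 15.9 days (168 h, the 7-day limit).

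**Step 2. Second model as a check.** With Poisson onsets at λ per day and 4-hour episodes, a clean recording needs no onset in the 24 + 4 hours that could overlap it: P = exp(−λ × 28/24). Daily: exp(−1.167) = 0.31. Weekly: exp(−0.167) = 0.85. Monthly: exp(−0.039) = 0.96. The daily range of 20-31% spans this model at 4 h and the step 1 model at 6 h. The step 1 model at 4 h gives 0.833 × exp(−1.2) = 0.25.

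**Step 3. If documented recurrences from day 90 to day 360 also count as failures.** There are 270/T episodes in those 270 days, each documented independently with chance q: P(success) = P(clean) × (1 − q)^(270/T). With 6-hour episodes:

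| Mean cycle | Episodes | q = 0 | 1% | 2% | 5% |
|---|---|---|---|---|---|
| Weekly | 38.6 | 83% | 56% | 38% | 12% |
| Monthly | 9.0 | 96% | 88% | 80% | 60% |

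The share drops below one half above q of about 1.3% (weekly) or 7.0% (monthly).

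**The case against.** **A reader might infer that most paroxysmal subjects with unchanged AF would pass.** The documents do not support that. It depends on a frequency and duration they do not state. It is true for roughly weekly or rarer episodes lasting up to about a day. It is false for near-daily episodes and for frequent multi-day ones. A mix weighted to daily 6-hour episodes (60% daily, 20% weekly, 10% monthly, 10% three-monthly) gives 0.6 × 0.198 + 0.2 × 0.832 + 0.1 × 0.959 + 0.1 × 0.986 = 48%.

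**The Holter may not be the whole endpoint.** A 90-day blanking period has no function for one recording made at day 346 to 374. The plan collects recurrences elsewhere, calls them lack of effectiveness, and plans a Kaplan-Meier analysis that implies later events are failures. Entry also requires symptoms, which make an unscheduled visit more likely. This objection has force: step 3 shows that a small documentation chance changes the answer. It does not dispose of the point, because section 4.2 names only the Holter, monitoring outside it is only as applicable, and the documentation chance is unknown. The readable text never says how to score a subject with a recurrence after day 90 and a clean month-12 Holter.

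**A reader might infer a badly inflated pooled rate.** Section 8.5 splits paroxysmal from persistent AF once more than 25% are paroxysmal. At that limit, weekly 4-hour episodes would contribute about 0.25 × 0.85 = 21 points to a pooled rate. Nor can one assume that persistent subjects never pass without an ablation effect, since procedural cardioversion and, in one definition, class I/III drugs are allowed.

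**Unseen material.** The CRFs are under separate cover, the table mock-ups cited in 8.2.1 are not in the public text, and parts of section 8 are blacked out. Episode frequency may already be recorded or used for stratification. The statement here is limited to the listed baseline items.

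**Conclusion.** The point holds in limited form. Read as worded, section 4.2 lets an unmeasured and possibly large share of paroxysmal subjects with unchanged AF be scored as long-term successes, and the listed data cannot show how large it is.

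Under the assumed patterns, and on the Holter alone, the share is about 20-31% (daily, 4-6 h), 73-87% (weekly, up to 24 h), about 45% (weekly, 72 h) and 93-97% (monthly, up to 24 h). These figures describe what the criterion would pass if AF were unchanged; they do not predict the study's result. They are upper values if documented recurrences after day 90 are also failures, so sections 4.2 and 8.2.1 have to be reconciled before any one figure can be quoted. The point concerns the paroxysmal group: AF that remained continuous would appear on the Holter.

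**What to change.** 1. In section 4.2 and Appendix XII, report the paroxysmal result as *arrhythmia-free on the month-12 24-hour Holter*. Place it beside the section 8.2.1 Kaplan-Meier freedom from any documented recurrence after day 90, and do not present the Holter figure alone as the long-term success rate. In the same edit, state how a documented recurrence after day 90 followed by a clean month-12 Holter is classified.
2. In section 6.1.1, under arrhythmia history, record the number and usual duration of AF episodes in the 3 months before consent, unless the CRF already does so.
3. Tabulate the month-12 Holter result in paroxysmal subjects by that baseline frequency.

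**Cost.** Wording in two places, two baseline fields and one table, with no added recording or procedure. The baseline fields are subject-reported and approximate, good enough to stratify by but not to build a modelled comparator on. The Kaplan-Meier figure has its own limit, since recurrence outside the Holter is found only when someone looks and need not pass through the core laboratory. The headline for paroxysmal AF becomes less favourable.

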4.3 Additional Evaluations

- Adverse events including any device-, procedure-, or death-related events.
- Rate of repeat ablations after study procedure during 12-month follow up defined as proportion of subjects with an additional ablation procedure to treat indicated cardiac arrhythmia (outside blanking period, if applicable).
- Change in quality of life (QOL) at 6 months and 12 months after receiving HD mapping and RF ablation relative to baseline: defined as change in quality of life assessed in the validated EQ-5D-5L QOL survey.

5.0 SUBJECT SELECTION AND WITHDRAWAL

5.1 Subject Population

This clinical investigation will enroll male and female subjects from the general AF population. Subjects must meet all eligibility criteria and provide written informed consent prior to conducting any study required procedures.

5.2 Subject Screening and Informed Consent

5.2.1 Subject Screening

Potential patients presenting at the clinical sites will be fully informed about the clinical investigation, following the established Informed Consent process (described in Section 5.2.2). Once a duly dated and signed Informed Consent form is obtained, the clinical investigation-specific screening procedures may begin.

Subjects must be screened for clinical investigation eligibility by a member of the site's clinical investigation team previously trained to the CIP, and if applicable will be entered into a site-specific screening log.

If the subject does not meet all inclusion criteria, or meets any of the exclusion criteria, the subject is considered a screening failure. The Principal Investigator or the delegated clinical investigation personnel will record the screening failure in the hospital records and on a screening log as required.

Clinical Investigation Plan

Patients who meet all inclusion criteria and none of the exclusion criteria are eligible to participate in this clinical study. Eligible patients presenting at clinical sites will be fully informed about the clinical study and asked to sign an Informed Consent form if they wish to participate in the clinical study. These patients will also be entered into the screening log.

The following assessments may need to be performed after obtaining consent and prior to the procedure as part of the screening process:

- Pregnancy test
- Intracardiac thrombus assessment

Subject data will be collected for the clinical study after obtaining signed Informed Consent form.

5.2.2 Informed Consent

A template Informed Consent form will be provided to each site by the Sponsor under separate cover for use in this clinical study. Site-specific language will be added to the template and approved by research personnel, the Sponsor, and governing EC prior for use in the trial.

The Investigator or his/her authorized designee (if applicable) will conduct the Informed Consent process, as required by applicable regulations and the center's EC. This process will include a verbal discussion with the subject on all aspects of the clinical investigation that are relevant to the subject's decision to participate, such as details of clinical investigation procedures, anticipated benefits, and potential risks of clinical investigation participation. Subjects must be informed about their right to withdraw from the clinical investigation at any time and for any reason without sanction, penalty or loss of benefits to which the subject is otherwise entitled. Withdrawal from the clinical investigation will not jeopardize their future medical care or relationship with the investigator.

During the discussion, the Principal Investigator or his/her authorized designee will avoid any improper influence on the subject and will respect subject's legal rights. Financial incentives will not be given to the subject. Subjects may be compensated for time and travel directly related to the participation in the clinical investigation. The subject shall be provided with the Informed Consent form written in a language that is understandable to the subject and has been approved by the center's EC. The subject shall have adequate time to review, ask questions, and consider participation. The Principal Investigator or his/her authorized designee will make efforts to ensure that the subject understands the information provided. If the subject agrees to participate, the Informed Consent form must be signed and dated by the subject and thereafter by the person obtaining the consent prior to any clinical investigation-specific procedures. The signed original will be filed in the subject's hospital or research charts, and a copy will be provided to the subject.

Failure to obtain informed consent from a subject prior to clinical investigation enrollment should be reported to Sponsor within 5 working days and to the reviewing center's EC according to the EC's reporting requirements.

If, during the clinical investigation, new information becomes available that can significantly affect a subject's future health and medical care, the Principal Investigator or his/her authorized designee (if applicable) will provide this information to the subject. If relevant, the subject will be asked to confirm their continuing informed consent in writing.

Clinical Investigation Plan

Special Circumstances for Informed Consent

Incapacitated individuals, defined as persons who are mentally ill, mentally handicapped, or individuals without legal authority, are excluded from the study population.

Individuals under the age of 18 or age of legal consent are excluded from the study population.

Individuals unable to read or write are excluded from the study population.

Pregnant or breastfeeding women are excluded from the study population.

5.3 Eligibility Criteria

5.3.1 General Eligibility Criteria

Assessment for general eligibility criteria is based on medical records of the site and interview with a candidate patient. If some of the clinical and laboratory tests are not included in site standard tests, they must be done but after written informed consent is obtained. Patients must meet ALL the inclusion criteria to be considered for the clinical investigation. If ANY of the exclusion criteria are met, the patient is excluded from the clinical investigation and cannot be enrolled.

5.3.2 Inclusion Criteria

General Inclusion Criteria

1. Subject must provide written informed consent for study participation and willing and able to comply with the protocol described evaluations and follow up schedule
2. Subject must be over 18 years of age. (In Japan, the subject must be of 20 years of age or older)
3. Subject is diagnosed with AF as defined by:
 - Documented symptomatic paroxysmal AF defined as AF that terminates spontaneously or with intervention within 7 days of onset
 - Documented symptomatic persistent AF defined as continuous atrial fibrillation that is sustained beyond 7 days but less than 12 months
4. Subject is indicated for cardiac electroanatomical mapping and RF ablation procedure to treat AF
5. Subject is planned to have electroanatomical mapping performed with the HD mapping catheters under investigation

5.3.3 Exclusion Criteria

General Exclusion Criteria

1. Previous ablation or surgery in the left atria
2. Implanted left atrial appendage occluder
3. Implanted mitral or tricuspid valve replacement
4. Implanted cardiac defibrillator (ICD)
5. Participation in another clinical investigation that may confound the results of this study

Clinical Investigation Plan

6. Pregnant or nursing
7. Presence of other anatomic or comorbid conditions, or other medical, social, or psychological conditions that, in the investigator's opinion, could limit the subject's ability to participate in the clinical investigation or to comply with follow-up requirements, or impact the scientific soundness of the clinical investigation results.
8. Life expectancy less than 12 months

5.4 Subject Enrollment

A subject is considered enrolled in the clinical study from the moment the patient provides written informed consent, has been confirmed to meet all inclusion criteria and none of the exclusion criteria, and a HD mapping catheter (i.e. Inquiry™ AFocusII™ Double Loop or Advisor™ HD Grid Sensor Enabled™) inserted.

5.5 Subject Withdrawal

Each enrolled subject shall remain in the clinical investigation until completion of the required follow-up period; however, a subject's participation in any clinical investigation is voluntary and the subject has the right to withdraw at any time without penalty or loss of benefit. Conceivable reasons for discontinuation may include, but not be limited to, the following:

- Subject death
- Subject voluntary withdrawal
- Subject lost-to follow-up as described below

The Sponsor must be notified of the reason(s) for subject discontinuation. The site will provide this information to the Sponsor. Investigators must also report this to their respective EC as defined by their institution's procedure(s).

No additional follow-up will be required or data recorded from subjects once withdrawn from the clinical investigation, except for the status (deceased/alive).

Lost-to-Follow-up

If the subject misses two consecutive scheduled follow-up time points and the attempts at contacting the subject detailed below are unsuccessful, then the subject is considered lost-to-follow-up. Site personnel shall make all reasonable efforts to locate and communicate with the subject (and document these efforts in the source documents), including the following, at each contact time point:

- A minimum of two telephone calls on different days over the specified follow-up windows to contact the subject should be recorded in the source documentation, including date, time and initials of site personnel trying to make contact.
- If these attempts are unsuccessful, a letter (certified if applicable) should be sent to the subject.
- If a subject misses one or more non-consecutive follow-up contact time points, it will be considered a missed visit. The subject may then return for subsequent visits. If the subject misses two consecutive time points and the above-mentioned attempts at communicating with the subject are unsuccessful, the subject will be considered lost-to-follow-up.

Clinical Investigation Plan

Note: Telephone contact with General Practitioner, non-clinical investigation cardiologist or relative without the presence of the subject or indirect documentation obtained via discharge letters will not be considered as subject contact.

[REDACTED]

[REDACTED]

[REDACTED]

